INVESTIGATIONAL PRODUCT OR PROCEDURE	Brief Behavioral Therapy for Insomnia (BBT-I) H ea l thy E ating E duc a tion L earning (HEAL)
PRIMARY OBJECTIVE(S)	The purpose of this study is to test the efficacy of brief behavioral therapy versus control condition that accounts for time and attention (nutrition education) in the treatment of insomnia in humans.
SECONDARY OBJECTIVE(S)	To assess the impact of different biomarkers on sleep disruption and other patient reported outcomes
TREATMENT SUMMARY	This research is designed to determine the efficacy of the BBT-I in comparison with the attention-matched behavioral control in reducing insomnia, fatigue, and cognitive difficulties in breast cancer patients. In addition, this study will examine the potential involvement of moderators (age, depression, anxiety, and hot flashes), specific behavioral mechanisms (maladaptive sleep behaviors, dysfunctional beliefs and attitudes), and physiological mechanisms (dysregulated circadian rhythms, disrupted wake-sleep cycles, and autonomic tone) as potential mediators of intervention-related changes in insomnia and the secondary outcomes of fatigue and cognitive difficulties. To address these aims, 180 breast cancer patients with acute insomnia during chemotherapy treatment will be recruited and randomized to receive either BBT-I or a behavioral control focused on healthy eating education. Each intervention condition will consist of 2 face-to-face sessions + 4 phone calls, delivered over a period of six weeks. Assessments will include sleep diary, questionnaires, neuropsychological testing, actigraphy, heart rate variability measurement, and salivary cortisol collection at baseline, post-intervention, and 6- and 12 months follow ups. By offering this intervention during

Behavioral Intervention for Insomnia in Cancer

	chemotherapy when patients are just beginning to develop insomnia, we hope to alleviate and avoid the development of chronic insomnia in the survivorship phase.
SAMPLE SIZE	180
STATISTICAL CONSIDERATIONS	The primary endpoint is insomnia. Secondary endpoints include cognitive functioning, fatigue, depression, HRV, cortisol and biomarkers of sleep and stress. The estimated power to detect the group difference in change in ISI is 0.88-0.99 (d=0.4 to 0.6, alpha=.05, two-tailed) with N=180 (90 BBT-I, 90 control).

Behavioral Intervention for Insomnia in Cancer

SCHEMA

LIST OF ABBREVIATIONS AND DEFINITION OF TERMS (Example)

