Expectancy/Feedback will be obtained by 2 checklists assessing the usefulness and acceptability of the experimental interventions and intervention outcome expectancy. Participants will complete the expectancy checklist at the end of their first face-to face session and feedback questionnaire at post-intervention to assess whether they found our interventions helpful for their symptoms. For these baseline variables that are not considered as potential moderators, given our strong design based on random assignment to treatment and control groups, it is reasonable to assume that they will be balanced between the intervention and control groups (i.e., no need to worry about controlling for them). Nonetheless, we will test sensitivity of our results to presence/absence of these potential baseline covariates, especially those that differ between groups due to natural experimental error.

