12.6.2 Sample size justification

For the primary Hypothesis 1 (BBT-I will show greater reduction of insomnia symptoms measured by ISI from baseline to the 12-month follow-up compared to the control), we estimated power in the proposed mixed effects modeling framework fully accounting for the longitudinal study design and projected attrition rate. The primary outcomes, ISI, will be measured at baseline, 6 weeks (end of treatment), 30 weeks, and 58 weeks (primary end point). For our power estimation, we used ML based mixed effects modeling assuming a linear trend. We assumed that at least 60% of variance is explained by the growth model for the primary outcome (i.e., reliability of 0.6), given that previous studies reported reliability ranging from 0.65-0.83.^{105,106} For attrition, we assumed gradually increasing attrition over time, resulting in 25% attrition by the 6-month follow-up assessment. We assumed a medium effect size, Cohen's d of 0.4 to 0.6, based on a previous study.¹⁰⁷ We also consider this range of effect size as the lower bound of a clinically meaningful treatment effect. Under this scenario, the estimated power to detect the group difference in change in ISI is 0.88-0.99 ($d=0.4$ to 0.6 , $\alpha=.05$, two-tailed) with $N=180$ (90 BBT-I, 90 control). We estimated power for the secondary Hypothesis 2 (BBT-I compared to the control will show greater improvements in fatigue and cognitive difficulties) using the same mixed effects modeling strategy. We assumed a moderate effect size of $d = 0.35$ to 0.4 , based on a previous study.^{108,109} We do not adjust for testing of multiple outcomes given that fatigue and cognitive difficulties are secondary outcomes. Under this scenario with reported reliability of 0.67 and higher,^{108,109} the estimated power to detect the group difference in change in BFI is 0.84-0.91 ($d=0.35$ to 0.4 , $\alpha=.05$, 2-tailed). For the mediator Hypothesis 3, we estimated power focusing on the main effect of the mediator on the outcome.^{98,99} We assumed a

Behavioral Intervention for Insomnia in Cancer

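### The primary ISI model fixes no prognostic baseline covariates, and the covariate sensitivity check stresses observed imbalance and is unclear about what counts as baseline

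*Combined protocol and SAP*

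**What the plan says.** - **Primary model (12.4.2).** A growth-curve mixed model by maximum likelihood uses ISI at baseline and weeks 6, 30 and 58, under intention to treat. Treatment status is the only predictor named. Baseline ISI enters as the first repeated measure. The section mentions baseline covariates to be collected but names none.
- **Covariates (10.1, expectancy and feedback paragraph).** Randomisation is taken to balance baseline variables that are not candidate moderators, so there is "no need to worry about controlling for them". The results are nevertheless to be tested with and without them, "especially those that differ between groups due to natural experimental error". There is no list, no definition of a difference, and no statement of which result prevails if they conflict.
- **What comes just before.** The same paragraph opens with expectancy and feedback: "Participants will complete the expectancy checklist at the end of their first face-to face session", and the feedback form is completed after the intervention. The next sentence speaks of 'these' baseline variables.
- **Related text.** Age, baseline anxiety and depression, emotion regulation and hot flashes are exploratory moderators (12.3, 12.5). Disease stage, chemotherapy type, prior treatment and receptor status are taken from the records, and current cancer treatment is recorded at each assessment to account for regimen differences (10.1). The nutrition knowledge questionnaire (NKQ) is to be used to control for attention (10.1) and is given at baseline and post-intervention (section 9).

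**The concern.** There are two weaknesses.

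First, a covariate improves the estimate to the extent that it predicts the outcome, not to the extent that it happens to differ between arms. Stressing the variables that turn out to differ ties the sensitivity results to chance. It also leaves the analyst to decide, with the data in hand, what counts as different. Randomisation is 1:1 with no stratification stated (12.1.1), so some imbalance should be expected. In addition, 12.4.2 and 12.5.1 cite baseline covariates in support of the missing-at-random approach, yet no covariate is placed in the model.

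Second, expectancy and feedback are measured after randomisation and can be changed by the intervention. Adjusting for them would remove part of the effect under study. A post-intervention NKQ score has the same problem, because the control arm is taught nutrition. The wording does not exclude any of the three.

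**Working it through.** **Inputs from the documents (12.6.2, 12.4.2).** 90 per arm, two-sided alpha 0.05, d = 0.4 to 0.6, reliability 0.6, assessments at weeks 0, 6, 30 and 58. On the model: "we used ML based mixed effects modeling assuming a linear trend". On dropout: "we assumed gradually increasing attrition over time, resulting in 25% attrition by the 6-month follow-up assessment". No 12-month attrition figure, slope variance or covariate R² is given.

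**Assumed.** Slope variance 0; a common baseline mean, so that treatment predicts change only; d defined on the week-58 difference; retention of 1 / 0.92 / 0.83 / 0.75 (pattern A) or 1 / 0.92 / 0.75 / 0.75 (pattern B).

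**1. The plan's own power.** Total variance is 1, of which 0.6 is stable between-person and 0.4 residual. The information matrix is the sum of n·f·X′V⁻¹X over arms and dropout patterns, where f is the share of patients in the pattern and V = 0.6·J + 0.4·I (J is the all-ones matrix). SE is the square root of the treatment-by-time element of the inverse. Power = Φ(d/SE − 1.96).

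- Pattern A, SE 0.1270: 0.4/0.1270 − 1.96 = 1.19, power 0.883; at d = 0.6, power 0.997.
- Pattern B, SE 0.1286: power 0.875 and 0.997.

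The plan states "the estimated power to detect the group difference in change in ISI is 0.88-0.99". The figure is reproduced to within about one point with no covariate beyond baseline ISI. It depends on the assumptions: dropout reaching 35-37.5% at week 58 gives 0.828-0.839 at d = 0.4, and arm-specific baseline means with dropout give 0.836-0.843.

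**2. Gain from fixed covariates.** Replace the stable variance 0.6 by 0.6 − R² (pattern A, d = 0.4). Equivalent extra patients = 180·[(0.1270/SE)² − 1].

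| R² (assumed) | SE | SE reduction | Power | Extra patients |
|---|---|---|---|---|
| 0 | 0.1270 | – | 0.883 | – |
| 0.05 | 0.1264 | 0.5% | 0.886 | about 2 |
| 0.10 | 0.1256 | 1.1% | 0.889 | about 4 |
| 0.20 | 0.1238 | 2.5% | 0.898 | about 9 |
| 0.30 | 0.1212 | 4.6% | 0.910 | about 18 |

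The gain is small because baseline ISI, as a repeated measure, already carries most of the stable between-person information.

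**3. How often something differs.** With K independent baseline variables each tested at 0.05, P(at least one differs) = 1 − 0.95^K. This is 0.23, 0.40 and 0.54 for K = 5, 10 and 15 (K assumed).

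**4. Imbalance as a criterion.** Simulation with one covariate, one time point, 67 per arm, d = 0.4, and covariate-outcome correlation 0.3 / 0.5 / 0.6:

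| Rule | Type I error | Power |
|---|---|---|
| Adjust only if imbalanced (p < 0.05) | 0.047 / 0.043 / 0.041 | 0.634 / 0.637 / 0.651 |
| Always adjust | about 0.05 | 0.669 / 0.751 / 0.821 |
| Claim success on either test | 0.064 / 0.071 / 0.078 | – |

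This compares rules in the abstract. It contains no repeated baseline ISI, so step 2 is the guide to the size of the gain in this trial.

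**5. If expectancy were adjusted for.** Adjusted effect = d − (arm difference in expectancy) × (its coefficient). With an assumed difference of 0.2-0.8 SD and coefficient of 0.1-0.3, d = 0.4 becomes 0.4 − 0.2·0.1 = 0.38 down to 0.4 − 0.8·0.3 = 0.16. Power falls from 0.88 to between 0.85 and 0.24. This is illustrative only.

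**The case against.** The other side has good arguments, and most of them stand.

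- **The primary analysis is not data-driven.** A reader might infer that covariates in the primary model will be chosen by imbalance. The text does not support this. The imbalance phrase is an emphasis inside a sensitivity analysis that covers all the potential baseline covariates, and the primary model is fixed. An unadjusted primary analysis is valid in a randomised trial. The inflated error in step 4 arises only if success may be claimed on either result, which the plan does not propose.
- **The rule excludes moderators.** Age and baseline anxiety and depression therefore fall outside it and already have an exploratory role. That role does not make them adjustment terms in the primary model.
- **Expectancy is not stated to be a covariate.** A reader might infer a plan to adjust for it. Yet the balance argument makes sense only for pre-randomisation variables, and 'these' may refer back to the medical variables in the preceding paragraph. The calendar's baseline mark for feedback proves little, because the calendar has no column for session 1. HEAL is also built to be credible, which works against a large expectancy gap. The ambiguity in the wording remains.
- **Precision.** A reader might apply √(1 − R²) to R² = 5-20% and infer an SE reduction of 2.5-10.6%, or 9-45 patients. That shortcut ignores the repeated baseline ISI. The growth model gives 0.5-2.5%, or about 2-9 patients.

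**Conclusion.** The point holds as a matter of pre-specification and clear wording, not as an error in the primary test. No prognostic covariate is fixed for the primary model, the sensitivity analysis stresses chance imbalance without a list or threshold, and its wording lets a literal reader count post-randomisation measures as baseline. Sample size and stated power do not change. The precision gain at d = 0.4 is about 0.3 to 1.5 power points (0.883 to 0.886-0.898) for an assumed R² of 5-20%, given zero slope variance and about 25% attrition at week 58. The possible loss from adjusting for expectancy is larger, but it rests wholly on assumed inputs and would affect only the sensitivity analysis.

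**What to change.** **In 12.4.2**
- Name a short, fixed set of pre-randomisation prognostic covariates already collected, for example age, baseline depression and anxiety (Clinical Assessment of Depression), and chemotherapy type at baseline. Include them in the mixed model whatever their balance.
- State whether they act on level only or also on slope.
- Make this the primary result and keep the unadjusted model as the sensitivity analysis.
- Settle the list before anyone sees outcomes by arm.

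**In 10.1**
- Delete the emphasis on variables that differ between groups, and say which variables 'these' refers to.
- State that expectancy, feedback and post-intervention NKQ are not adjustment covariates in the efficacy analysis.
- Say how the cancer treatment recorded at each assessment will be used, since values after baseline are also post-randomisation.

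Age and the baseline mood measures can stay exploratory moderators. The cost is a few sentences of SAP wording and a slightly more complex model. No new data or patients are needed.

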10.1.1 Relevant Subset

N/A

10.1.2 Measurement Definition

The measurement is self-report of changes in symptomatology.

10.1.3 Measurement Methods

The measures are self-report (questionnaires), objective (actigraphy, saliva, heart rate monitor, blood sample).

10.1.4 Measurement Time Points

Baseline, 6 weeks, 6 months and 12 months.

10.1.5 Response Review

N/A

10.2 Secondary Outcome

Described in section 10.1.

11. REGULATORY CONSIDERATIONS

11.1 Institutional Review of Protocol

The protocol, the proposed informed consent and all forms of participant information related to the study (e.g. advertisements used to recruit participants) will be reviewed and approved by the Stanford IRB and Stanford Cancer Institute Scientific Review Committee (SRC). Any changes made to the protocol will be submitted as a modification and will be approved by the IRB prior to implementation. The Protocol Director will disseminate the protocol amendment information to all participating investigators.

11.2 Data and Safety Monitoring Plan

The Stanford Cancer Institute Data and Safety Monitoring Committee (DSMC) will be the monitoring entity for this study. The DSMC will audit study-related activities to determine whether the study has been conducted in accordance with the protocol, local standard operating procedures, FDA regulations, and Good Clinical Practice (GCP). This may include review of the following types of documents participating in the study: regulatory binders, case report forms, eligibility checklists, and source documents. In addition, the DSMC will regularly review serious adverse events and protocol deviations associated with the research to ensure the protection of human subjects. Results of the DSMC audit will be communicated to the IRB and the appropriate regulatory authorities at the time of continuing review, or in an expedited fashion, as needed.

11.3 Data Management Plan

The Protocol Director, or her designee, will prepare and maintain adequate and accurate participant case histories with observations and data pertinent to the study. Study specific Case

Behavioral Intervention for Insomnia in Cancer

Report Forms (CRFs) will document treatment outcomes for data analysis. Case report forms will be developed using the Qualtrics and SPSS database system and will be maintained by the data manager. CRFs will be kept in a locked office, only accessible to the research team.

12. STATISTICAL CONSIDERATIONS

12.1 Statistical Design

This is a 2 arm randomized control clinical trial phase III.

12.1.1 Randomization

After consent has been obtained, patients will be randomized 1:1 by a computerized random number generator to one of two arms: BBT-I or HEAL. In order to ensure blinding of assessors, only the data manager, intervener delivering intervention and clinical intervention supervisor will know the randomization assignment. All other study staff will be blinded.

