3.4 Randomization Procedures

Participants will be randomized into one of two arms: BBT-I or HEAL. The study data manager will use a computerized random number generator to assign participants into arms. In order to keep study blinded from assessors, only the interventionist providing the intervention, the data manager, and the clinical intervention supervisor will know randomization.

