5. INVESTIGATIONAL PROCEDURE INFORMATION

5.1 Investigational Procedure

BBT-I Intervention Group: 90 BC patients will be randomized to receive the BBT-I. BBT-I includes both stimulus control and sleep scheduling, however it has been modified from CBT-I to make it more suitable for cancer patients undergoing chemotherapy with recently developed sleep problems. The main intervention component is one face-to-face 60-minute session with a trained staff member during which time an individually tailored “sleep prescription” is developed. There will also be four 15-minute phone calls and a second 60-minute face-to-face “booster” session. The second face-to-face session will ideally occur during the third or fourth week depending on the patient’s chemotherapy regimen.

BBT-I is a novel intervention that applies innovative cancer-specific chronorehabilitation techniques to effectively treat acute insomnia among patients receiving chemotherapy in the infusion clinic. It is comprised of the following four components: 1) **chronorehabilitation education** (e.g., information on the contribution of circadian disruption to insomnia in the context of cancer and cancer treatment, a review of the cancer-specific behavioral model of insomnia, and discussion regarding how insomnia and fatigue may co-occur and interact.); 2) **light and stimulus control** (e.g., decrease light exposure at night and increase light exposure during the day, do not go to bed until sleepy, and get out of bed if not sleeping); 3) **encouragement of physical activity and discouragement of napping** (e.g., increase exercise and limit naps to 2 per day and no longer than 45 minutes); and 4) **sleep compression** (e.g. increasing motivation to regulate sleep and wake cycles, and go to bed later by at least 15 minutes if sleep efficiency is less than 85%). Patients are told that on their sick days (e.g., days post chemotherapy) they can nap and sleep as much as they need to. In our pilot, we found that patients successfully moderated their sleep prescription on the days when they were not feeling well.

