6. DOSE MODIFICATIONS

Half of the participants will be randomized to BBT-I and the other half will be randomized to HEAL. Both groups will receive 6 sessions. There will be no modification in the number of sessions received.

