12.6 Sample Size

12.6.1 Accrual estimates

Stanford Cancer Center sees approximately 500 new breast cancer patients per year and about 341 patients (Range 318-376) are currently undergoing chemotherapy per STRIDE database. In our pilot, we were able to recruit a new participant every week. Thus, we anticipate that we would be able to meet our recruitment goal within 4 years even after accounting for attrition.

To minimize attrition, we will schedule participants for assessments during their clinic days. We budgeted funds for participants' travel, parking, and refreshments to improve retention. We will maintain close contact with participants with letters and projects updates, call or email (based on their preference) to remind participants to follow the study procedures. We also will send birthday cards and provide recruitment updates on our website to keep participants interested throughout the duration of the study. The proposed study involves a lower participant burden than our pilot that required more follow-ups, longer actigraphy and saliva collection and more measures. We found that we were able to minimize attrition in our current pilot with the above mentioned strategies. We will work closely with the Breast Cancer Connections advocacy group as we have done in the past, to provide training to our staff to ensure supportive and rewarding experiences for our participants. We will monitor our accrual closely and based on our current experience, we anticipate being able to recruit our participant sample. However, if we are unable to meet our recruitment target during the first year, we will expand our recruitment area to other local oncology clinics.

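### The plan states no blocks or strata, trusts randomisation alone for balance, and leaves the primary ISI model without pre-specified baseline adjustment

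*Combined protocol and SAP*

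**What the plan says.** Allocation is described twice. Section 3.4 says "The study data manager will use a computerized random number generator to assign participants into arms". Section 12.1.1 adds the ratio: "patients will be randomized 1:1 by a computerized random number generator". Neither mentions blocks, strata, minimisation or site, and neither rules them out. Elsewhere the split is given as equal: "90 BC patients will be randomized to receive the BBT-I" (Section 5.1, with the same number for HEAL) and "Half of the participants will be randomized to BBT-I and the other half will be randomized to HEAL" (Section 6).

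For baseline variables that are not candidate moderators, Section 10.1 argues from random assignment that "it is reasonable to assume that they will be balanced between the intervention and control groups", and concludes that controlling for them is unnecessary. It then promises to check whether results change with and without such covariates, with emphasis on those that turn out to differ between the arms.

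Section 12.4.2 fits a growth curve to ISI at weeks 0, 6, 30 and 58. Change is the dependent variable and treatment status is the only predictor named. The text does not say whether the arms share one baseline mean or have separate ones.

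Entry (Section 3.1) admits any ISI of 8 or more, and treatment with either chemotherapy or biologics. If first-year recruitment falls short, Section 12.6.1 says "we will expand our recruitment area to other local oncology clinics".

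**The concern.** Balance under randomisation is a property of the average over repeated trials. In one trial of 180 women, sizeable gaps on individual factors are common unless the design or the analysis deals with them. The plan describes no restriction on the allocation, and it gives balance as the reason not to adjust. Baseline ISI is collected anyway and treatment type is taken from the records. Not using them in the primary model gives up precision, and leaves the one estimate that will be reported open to whatever imbalance occurs.

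**Working it through.** **1. The plan's own power figure.** Section 12.6.2 gives 0.88 to 0.99 for d = 0.4 to 0.6, with N = 180, two-sided alpha 0.05, a linear trend, reliability 0.6 and 25% attrition by 6 months. Slope variance, intercept-slope covariance, 12-month attrition and the scaling of d are not given, so the figure cannot be reproduced uniquely. I assumed zero slope variance, attrition held at 25% to 12 months, and d as the week-58 arm difference in total-SD units. Power is Φ(d/SE − 1.96).

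- Common baseline mean: SE = 0.1285; power = Φ(0.4/0.1285 − 1.96) = Φ(1.15) = 0.875, and 0.997 at d = 0.6.
- Separate baseline means: SE = 0.1361; power = Φ(0.4/0.1361 − 1.96) = Φ(0.98) = 0.836, and 0.993 at d = 0.6.

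The stated figure is therefore not shown to be wrong; one plausible set of inputs comes within a point of it. Under these inputs a common baseline mean is worth about 4 points of power at d = 0.4, with variance ratio (0.1285/0.1361)² = 0.89. With slope variance of 0.1 to 0.3 (assumed), power at d = 0.4 is 0.82 to 0.71 with a common baseline and 0.78 to 0.68 without.

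**2. Arm sizes, if the draw is simple.** The arm size is Binomial(180, 0.5).

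- P(exactly 90/90) = 0.059. The 95% range is 77 to 103 per arm. P(100/80 or worse) = 0.157.
- Relative efficiency at 103/77 is 4 × 103 × 77/180² = 0.979.
- With the SD calibrated so that 90/90 gives 0.880 at d = 0.4, power is 0.876 at 100/80 and 0.873 at 103/77. The loss is at most 0.7 points within the 95% range.

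**3. Chance imbalance in one covariate.** The standardised difference between arms has SD √(4/180) = 0.149.

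- P(gap > 0.2 SD) = 2Φ(−0.2/0.149) = 0.18.
- P(gap > 0.25 SD) = 2Φ(−0.25/0.149) = 0.094.
- For a yes/no factor with prevalence p the SD is √(4p(1−p)/180). P(gap > 10 percentage points) is 0.09, 0.14 and 0.18 at assumed prevalences of 20%, 30% and 50%.

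**4. What a baseline ISI gap does to the estimate.** Let the arms differ by δ at baseline by chance, and let r be the baseline-to-follow-up correlation (not in the documents; assumed 0.3 to 0.7). The follow-up difference is expected to carry rδ, so an unadjusted change contrast moves by (1 − r)δ, in favour of the arm that started worse. With δ = 0.25 SD:

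| r | shift in the change contrast |
|---|---|
| 0.3 | 0.7 × 0.25 = 0.175 SD |
| 0.5 | 0.5 × 0.25 = 0.125 SD |
| 0.7 | 0.3 × 0.25 = 0.075 SD |

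This is the two-visit result. A straight line through all four visits dilutes it. With complete data and zero slope variance the factor is 23.5 × 58/2091 = 0.65, where 23.5 is the mean visit week and 2091 the sum of squares of the visit weeks about that mean. The shift is then about 0.05 to 0.11 SD. A common baseline mean largely removes the shift.

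**5. Whether the plan already covers this.** The Section 10.1 sensitivity analysis names no covariates, gives priority to those that differ after randomisation, and sits outside the primary model. It does not say which result stands if the adjusted and unadjusted answers disagree.

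**The case against.** The case against has several sound parts.

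- A computerised generator can produce a blocked or stratified list, and the half-and-half wording fits a restricted list or a nominal target. This stands: the documents are silent on restriction, and the figures in steps 2 and 3 apply only if the draw is simple.
- Chance imbalance is not bias. Under simple randomisation the contrast is unbiased on average, and its standard error already allows for such gaps. This also stands.
- Baseline ISI is already one of the four outcomes in the growth curve. That helps only if the arms are held to a common baseline mean, which Section 12.4.2 does not state.
- Age, depression, anxiety, hot flashes and emotion regulation are examined as moderators or non-specific predictors (Sections 12.3 and 12.5). Section 10.1 also records treatment at each assessment to allow for regimen differences. Both are true, but the moderator work is exploratory, and Section 12 gives treatment type no role in the primary model.
- Extra clinics are a contingency. Section 12.6.1 expects to meet the target without them, so a site term is needed only if one opens.

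**Conclusion.** The point holds as a gap in the analysis plan. The primary ISI estimate is left without pre-specified adjustment for prognostic values that the trial collects, on the ground of a balance that no stated feature of the allocation secures.

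The size is moderate: an 18% chance of a gap above 0.2 SD per continuous covariate, and a shift of 0.075 to 0.175 SD from a 0.25 SD gap in baseline ISI, less with a four-visit straight line. This rests on a simple draw, an assumed r of 0.3 to 0.7, and arms with separate baseline means.

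A reader might infer more, in three ways that the documents do not support:

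- That the allocation is known to be unrestricted. It is only unspecified.
- That missing 90/90 undermines the trial. It costs under one point of power and leaves the type I error valid.
- That a chance gap would account for a fixed share of the planned d of 0.4 to 0.6. That would need a single value of r and the scaling of d, and the plan gives neither.

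**What to change.** In Section 12.4.2, pre-specify that the primary ISI growth model:

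- holds the arms to a common baseline mean, or uses baseline ISI as a covariate with post-baseline outcomes only (the first option keeps the plan's rule of including every woman with at least one assessment);
- adjusts for treatment type at entry (chemotherapy versus biologic without chemotherapy), as a predictor of both level and change;
- adjusts for site if a second clinic opens.

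Replace the Section 10.1 statement that control is unnecessary with a reference to this list, and keep the unadjusted model as the sensitivity analysis. The cost is a short text amendment, with no new data and no extra patients.

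State the type of randomisation in Sections 3.4 and 12.1.1. If a restricted list is already in use, this only corrects the text. Optionally, use permuted blocks of varying size with few strata, for example treatment type, and site if one is added. Blocking secures arm sizes, not covariate balance, so it does not replace the adjustment. Its small downside is that assignments become slightly more predictable to unblinded interventionists, which varying block sizes limit.
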